- Singleton pregnancy.
- Gestational age between 37 completed weeks to 42 weeks.
- Patients undergoing elective primary caesarean section

Exclusion criteria:

- History of uterine surgery (e.g. hysterotomy, myomectomy, perforation, caesarean section). (to be able to differentiate between the recent CS scar and the old scar)
- Abnormal placental invasion (placenta previa and accrete) (more liable to undergo Cesarean hysterectomy)
- Uterine anomalies (e.g., septum, Mullerian anomalies or fibroids). (may be localized at the suture line and therefore affect the scar)

- Drugs intake that affects bleeding or tissue healing e.g., anti-coagulants, immunosuppressive drugs and chronic use of steroids (more than 14 days pre-operative)
- Any medical Co-morbidity (diabetes mellitus, Hypertension and Thyroid abnormalities) (more liable to affect the healing)

● **Randomization:**

Randomization will be done using computer generated random sequence. Study population will be randomized into one of the two groups:

- Group (I): 70 patients will undergo uterine closure using Monofilament suture material. (A) (1/0, Monocryl®).
- Group (II): 70 patients will undergo uterine closure using Multifilament suture material. (B) (1/0, Vicryl®).

● **Allocation concealment:**

One hundred and forty opaque envelopes will be numbered serially and each envelope with the corresponding number which denotes the allocated group will be put according to randomization table. Then all envelopes will be closed and put in one box. When the first patient is included, the first envelope will be opened and the patient will be allocated according to the letter inside.

● **Blinding:**

Double blinding is difficult because the surgeon will perform the procedure. However, the measured outcomes are objective and unlikely to be biased by lack of blinding. Patient is blinded, sonography (measuring the outcome is blind to type of repair). Statistical analysis will be blinded to group allocation (single blinded)

● **Study procedures and interventions:**

The patients will be randomly divided into 2 groups using a computer-generated number based on the type of suture materials to be used for the continuous double-layer unlocked closure of the low transverse uterine incision during Cesarean section.

Surgery will be done by the most senior resident.

Baseline Evaluation

All participants will be submitted to:

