- Skin closure: Reapproximation of the skin will be performed with subcuticular suture using 2-0 polypropylene nonabsorbable suture (EGYPROLENE® manufactured by Taisier-Med Obour city, Cairo, Egypt.).

Post-operative care:

- All patients will receive Non-Steroidal Anti-Inflammatory drugs immediately postoperative then one ampoule 12 hours postoperative, (**Altman, 2015**). and according to Ain Shams Maternity hospital protocol.
- Vital signs (pulse, blood pressure, temperature) of the patients will be measured four times daily during hospitalization.
- At 6 h postoperatively, urinary Foley catheters will be removed and oral intake with clear fluids will be started. (**ACOG, 2008**).
- A venous blood sample for complete blood count examination will be withdrawn after 24 hours postoperative.
- Regular antipyretic will not be used so as not to mask possible postpartum pyrexia.

- Patients will be instructed for postoperative wound care e.g.: to always keep wound dressing dry and clean and in case it gets wet it is to be dressed in an aseptic non-touch technique.
- Follow up for assessment after 1 week of delivery to check the wound, and after 6 months to undergo the Ultrasound.

Outcomes:

Primary outcome: the incidence of isthmocele by transvaginal ultrasound 6 months after delivery.

Isthmocele is defined as an anechoic defect communicating with the endometrial cavity at the anterior wall of the lower uterine segment.

For each case the following isthmocele measurements will be obtained:

1. The thinning extent, calculated by a ratio between (a) and (b).
 - (a): thickness of the residual myometrium over the defect.
 - (b): total intact myometrium. A severe deficiency occurs when more than 50% of myometrium is lost at the niche scar site.
2. Width of isthmocele (c)
3. Depth of isthmocele (d)

Furthermore, we will record the shape of the defect (i.e., triangular, round, or oval). Moreover, the residual myometrial thickness will be measured. In case of isthmocele, RMT overlying the defect and the adjacent myometrial thickness fundal to the defect will be recorded. According to previous literature, the diagnosis of isthmocele was made in case of depth of the defect at least 2.00 mm in the longitudinal plan. (**Naji O et al, 2012**).

[figure not shown]

Figure 1.

Secondary outcomes:

1. Amount of blood loss.

ABL = weight kg * age sex factor (65ml/ kg)*initial HGB(g/dl)-final HGB(g/dl) / 12-hours postoperative"./ intial HGB (g/dl) (M. E. Brecher,2003)

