2. Need for extra hemostatic sutures.
3. Need for blood transfusion.

4. Wound infection.
5. Hospital stay after the delivery.
6. Post-operative fever.

(Defined as a temperature higher than 38 c on two consecutive postoperative days or higher than 39 c on any postoperative day). **(Abdelmaseeh TA et al, 2022)**

7. Primary Postpartum hemorrhage. (Defined as Cumulative blood loss greater than 1000 mL with signs and symptoms of hypovolemia within 24 hours of the delivery). **(ASOG,2017)**.

- **Statistical analysis:**

Based on the results of Saccone et al 2022 , with the mean defect width in mm in monofilament group 2.9 ± 0.6 and in multifilament group 3.4 ± 1 mm, alpha error 5% and power of study 80%, the required sample is 140 patients 70 in each group . The program for sample size calculation is STATA 10.

- **Ethical Consideration:**

This study will be done after approval of the ethical committee of the department of obstetrics and gynecology, faculty of medicine, Ain Shams University. Informed consent will be taken from all participants before recruitment in the study, and after explaining the purpose and procedures of the study. The investigator will obtain the written, signed informed consent of each subject prior to performing any study specific procedures on the subject. The investigator will retain the original signed informed consent form. All laboratory specimens, evaluation forms, reports, and other records that leave the site will not include unique personal data to maintain subject confidentiality. The study will be based on the investigator self-funding.

Protocol approval:

Before the beginning of the study and in accordance with the local regulation followed, the protocol and all the corresponding documents will be declared for ethical and research approval by the council of OB/GYN Department, Ain Shams University according to the the ethical committee

Patient right to withdraw

4. REFERENCES:

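### The protocol calls all measured outcomes objective, but extra haemostatic sutures are the unblinded surgeon's own decision, and the claim is unsupported for wound infection, transfusion and hospital stay

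*Protocol*

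**What the plan says.** The Blinding paragraph (Protocol, section 3, Methodology) starts from the surgeon: "Double blinding is difficult because the surgeon will perform the procedure". It then states "However, the measured outcomes are objective and unlikely to be biased by lack of blinding", without limiting this to the ultrasound. The parties named as blind are the patient and the sonographer ("Patient is blinded, sonography (measuring the outcome is blind to type of repair") and the analysis ("Statistical analysis will be blinded to group allocation (single blinded"). No one else is named.

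The primary outcome is isthmocele on transvaginal ultrasound at 6 months. The seven secondary outcomes include "Need for extra hemostatic sutures", the need for transfusion, "Wound infection" and "Hospital stay after the delivery". The list gives no criterion for any of these four, whereas fever and postpartum haemorrhage each carry a definition. Post-operative care provides for "Follow up for assessment after 1 week of delivery to check the wound" but does not say who does the check or whether that person is masked.

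**The concern.** An outcome is protected from knowledge of allocation if it is measured by an instrument or fixed rule, or if the person who determines it does not know the group. The Blinding section relies on the first protection for every outcome. For a decision taken by the operating surgeon, neither protection is present.

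The protocol itself records expectations that could act on such decisions. Its Introduction says that careless handling can weaken a monofilament and make it fail early, and credits the multifilament with more strength and easier tying. It also links the multifilament to more wound infection. A surgeon who holds these views could add stitches more readily in the monofilament arm. A wound examiner who knew the group could call infection more readily in the multifilament arm.

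At stake is how differences in these secondary outcomes are read. With the sentence as it stands, a difference in extra sutures could be taken as a property of the material when part of it reflects the surgeon's threshold.

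**Working it through.** The protocol gives no figure on this point to reproduce. The check sets the blinding statement beside each outcome.

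| Outcome | What determines it | Is that party named as blind? | Does the claim hold? |
|---|---|---|---|
| Isthmocele and niche measurements (primary) | Sonographer at 6 months | Yes | Protected by masking |
| 1. Blood loss | Formula from weight and haemoglobin | Not needed | Largely yes |
| 2. Extra haemostatic sutures | Operating surgeon, no criterion | No; surgeon must know the suture | No |
| 3. Transfusion | Clinical decision, decision maker not named | Not stated | Unsupported |
| 4. Wound infection | Clinical judgement, assessor not named | Not stated | Unsupported |
| 5. Hospital stay | Discharge decision, decision maker not named | Not stated | Unsupported |
| 6. Fever | Temperature thresholds | Not needed | Largely yes |
| 7. Primary postpartum haemorrhage | Volume threshold plus signs and symptoms of hypovolaemia | Not stated | In part |

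Of the seven secondary outcomes, the claim fails for one, is unsupported for three, holds in part for one and largely holds for two (1 + 3 + 1 + 2 = 7).

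**Could the 1-week wound check be masked?** Under Operative steps, the arms differ only in the uterine suture. Fascia (Vicryl 1), the subcutaneous layer (Vicryl 0, when at least 2 cm) and skin (2-0 polypropylene) are closed the same way in both groups. The visible wound therefore does not reveal the allocation, and an examiner would learn it only from the records or from having been at the operation. The Case Record Form has a Group line on the same form as wound infection, hospital stay and postpartum haemorrhage, but the protocol does not say who completes it or sees it.

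**Illustration of size, on assumed rates only.** Suppose extra sutures are truly needed in 15% of each arm, and a lower threshold in one arm raises its recorded rate to 25%.

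- Expected counts: 0.15 × 70 = 10.5 and 0.25 × 70 = 17.5.
- Apparent relative risk: 17.5 / 10.5 = 1.67, with no true difference.
- Uncorrected chi-squared test: 10 v 18 of 70 gives 2.86 (p about 0.09); 11 v 17 of 70 gives 1.61 (p about 0.21).

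Over a range of assumed base rates, with 70 per arm, a two-sided 5% test and no true difference, the normal approximation gives these chances of a significant result in the direction of the shift:

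| Base rate | Shift of 3 points | Shift of 5 points | Shift of 10 points |
|---|---|---|---|
| 5% | 11% | 20% | 51% |
| 10% | 8% | 14% | 38% |
| 20% | 6% | 11% | 28% |

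The nominal chance in one direction is 2.5%. The approximation is rough at the lowest rates, where about 3.5 events per arm are expected. These figures show what a shift would do. They are not evidence that one would occur.

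**The case against.** The strongest reply is that the comparison that matters is protected. The aim and the research question concern isthmocele only, and a sonographer blind to the type of repair provides the primary outcome and all niche measurements. The disputed sentence stands next to the statement on the blinded sonographer and may have been written with that outcome in mind. This stands, and it confines the point to secondary outcomes. It does not rescue the sentence, which refers to the measured outcomes without restriction.

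A reader might infer that four of the seven secondary outcomes are biased by an unblinded team. The documents do not support that. Only the surgeon is shown to know the suture. For ward staff and the 1-week examiner the protocol is silent, the Group line on the Case Record Form does not show who sees it, and the abdominal wound looks no different by arm. Transfusion and days in hospital are also plainly recordable events; only the decisions behind them are open to influence. What remains is that an assurance is given for these outcomes without any stated basis.

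It is also fair to object that the 15% and 25% rates are invented and that, on those rates, the result would not usually be significant. They serve as an illustration only.

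Finally, the absence of a wound-infection definition is a separate question of detail that would arise under full blinding too. It may be settled elsewhere and forms no part of this point.

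**Conclusion.** The statement that the measured outcomes are objective and unlikely to be biased is wrong for extra haemostatic sutures. This follows from the text alone: the protocol says that the surgeon is not blinded, and the outcome is the surgeon's own choice. The statement is unsupported for wound infection, transfusion and hospital stay, because they rest on judgement and the protocol neither names those who judge as blinded nor says whether they know the group.

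A reader might go further and infer that the main result is at risk. It is not: the blinded sonographer protects it. The documents also do not show that bias will occur or how large it would be. Severity is minor, confined to secondary outcomes, and the correction is mainly one of wording and simple masking.

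**What to change.** 1. In the Blinding section, limit the statement on objectivity to the blinded 6-month ultrasound and to laboratory or temperature-based outcomes.
2. State that extra haemostatic sutures is an open-label, surgeon-determined outcome, and interpret it as such. It cannot be masked.
3. Have the 1-week wound check done by existing staff who were not at the operation, working from ward and clinic notes that do not name the uterine suture. Keep the Group line of the Case Record Form out of their view. Identical abdominal wall closure makes this feasible.
4. Notes without the suture name also reduce the risk for transfusion and hospital stay. Where staff may still know the group, say so when reporting these outcomes.

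The cost is a wording change and some care with the notes, with no extra visit. The downside is that the suture name must stay retrievable for clinical need. The protocol does not show whether operating and follow-up staff are separate. If they cannot be separated, the wound outcome should be described as unmasked.

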In this study we aim at comparing using synthetic absorbable monofilament sutures in uterine closure during caesarean delivery with using synthetic absorbable multifilament sutures as regards the reduction in the rate of isthmocele.

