An internationally recognized definition for isthmocele was only agreed upon in 2019 by the European task force, which defined a cesarean scar defect as an “indentation at the site in the cesarean section scar with a depth of at least 2 mm.” This definition was further subclassified as follows: simple niche, simple niche with one branch, and complex niche (with more than one branch). A branch was defined as the thinner part of the main niche that is directed toward the serosa and has a width smaller than the main niche. Residual myometrial thickness "RMT" is the distance between the tip of the hypo echoic triangle and the surface of anterior uterine wall measured by mm.) At the apex of the main niche, the RMT is often decreased. (**Jordans IPM et al,2019**).

The present study aimed to evaluate how the use of Monocryl (monofilament synthetic

absorbable sutures) instead of Vicryl (multifilament synthetic absorbable sutures) in the continuous double-layer unlocked closure technique for low transverse uterine incisions impacts uterine scar healing after Cesarean section.

2.AIM / OBJECTIVES

To evaluate the impact of using synthetic absorbable monofilament sutures in uterine closure during caesarean delivery compared to using synthetic absorbable multifilament sutures on the development of Isthmocele.

Research Question:

Will uterine closure using synthetic absorbable monofilament sutures during caesarean delivery reduce the incidence of isthmocele compared to uterine closure using synthetic absorbable multifilament sutures?

3.METHODOLOGY:

Patients and Methods/ Subjects and Methods/ Material and Methods

- **Study Type:** A Randomized Controlled Trial.
- **Study Setting:** The study will be conducted at Ain Shams University Maternity Hospital (labour ward and the Ultrasound (Special Care unit for the fetus).
- **Study Period:** 1 year. (from December 2023 to December 2024)
- **Sampling Method:** Convenience sample from El-Demrdash hospital population that attending the ER.
- **Study Population:** The study will be conducted on (140) women divided into two equal groups.
- **Sample Justification:** Based on the results of **Saccone et al. (2022)**, with the mean defect width in mm in monofilament group 2.9 ± 0.6 and in multifilament group 3.4 ± 1 mm, alpha error 5% and power of study 80%, the required sample is 140 patients 70 in each group. The program for sample size calculation is STATA 10.

Inclusion criteria:

- Age: 20-45 years old

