Chorioamnionitis in that pregnancy	
Medical history	
Surgical history	
Pre-operative haemoglobin level	
Post-operative haemoglobin level	
Total blood loss	
Number of received blood components	
Procedure time	

ICU admission	
Hospital stay	
Post-operative fever	
Wound infection	
Trans vaginal US after 6 months → Isthmocele? Yes or NO if Yes → Isthmocele measurements will be obtained.	
Bladder injury in that Cesarean section	
Post-partum hemorrhage

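### The 80% power is calculated for mean defect width, but the primary outcome is the incidence of isthmocele; nor does 80% follow from the width inputs

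*Protocol*

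**What the plan says.** The question is posed as a proportion throughout. The opening statement of aim compares the two sutures "as regards the reduction in the rate of isthmocele". The Research Question asks whether monofilament closure will "reduce the incidence of isthmocele compared to uterine closure using synthetic absorbable multifilament sutures". The Outcomes section gives "Primary outcome: the incidence of isthmocele by transvaginal ultrasound 6 months after delivery". The Case Record Form has a yes/no field for isthmocele at the 6-month scan and adds that, if the answer is yes, "Isthmocele measurements will be obtained".

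The sample size rests on a different variable. Sample Justification (section 3, Methodology) takes from an earlier trial a "mean defect width in mm in monofilament group 2.9 ± 0.6 and in multifilament group 3.4 ± 1 mm", sets "alpha error 5% and power of study 80"%, and concludes that "the required sample is 140 patients 70 in each group". The Statistical analysis paragraph repeats this and gives no other calculation. Nowhere does the protocol state an expected incidence in either arm, a difference in incidence to be detected, or an allowance for loss before the 6-month scan.

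**The concern.** A power figure belongs to one variable, one effect size and one test. Here it belongs to a difference in mean width, while the trial will be judged on a difference in proportions. Power for a proportion depends on the control rate and the target reduction, and neither is given. A reader will nevertheless take 80% as the power of the primary comparison. If the true power is much lower, a non-significant incidence result could be misread as evidence that suture material makes no difference.

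The width calculation also looks wrong on its own terms: a 0.5 mm difference with these standard deviations should need well under 70 per arm. And a woman without a defect has no defect width, so 70 women per arm need not supply 70 widths.

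**Working it through.** **Inputs from the protocol.** Width means 2.9 and 3.4 mm (difference 0.5); SDs 0.6 and 1.0; alpha 5%, taken as two-sided because the protocol does not say; power 80%; 70 per arm, allocated 1:1.

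**Step 1. The protocol's own figure.** Normal formula for two means:

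n per arm = (1.96 + 0.84)² × (0.6² + 1.0²) / 0.5² = 42.7, so 43 per arm.

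With the Welch t test (noncentral t), 44 per arm give 80.1% power and 70 per arm give 94.5%. The stated 70 is therefore not reproduced at 80%. A one-sided test moves further away (34 per arm). Loss alone would have to be 1 − 43/70 = 39% to turn 43 into 70. One route does give exactly 70: SD 1.0 in both arms gives 63, and 63/(1 − 0.10) = 70. The protocol states neither of these steps.

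**Step 2. Width when only women with a defect are measured.** The incidence is assumed. Welch t test:

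| Incidence in both arms | Widths per arm | Power | Power if the monofilament arm has 30% fewer defects |
|---|---|---|---|
| 30% | 21 | 48% | 44% |
| 40% | 28 | 60% | 56% |
| 50% | 35 | 70% | 66% |

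Power is 80% only if about 44/70 = 63% of women in each arm have a defect.

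**Step 3. Incidence, the primary outcome.** The control incidence is assumed. Exact enumeration of two binomials, pooled z (chi-square) test, two-sided 5%, 70 vs 70, no loss:

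| Control incidence | Power, 30% reduction | Power, one-third reduction | Power, halving | Monofilament incidence detectable with 80% power | Relative reduction |
|---|---|---|---|---|---|
| 20% | 16% | 18% | 38% | 5.0% | 75% |
| 30% | 23% | 28% | 58% | 11.3% | 62% |
| 40% | 32% | 39% | 75% | 18.8% | 53% |
| 50% | 43% | 52% | 87% | 27.1% | 46% |
| 60% | 58% | 67% | 95% | 36.7% | 39% |

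At 70% control incidence a one-third reduction just reaches 80%. Loss makes every row worse: with 60 per arm scanned and 40% control incidence, the detectable monofilament incidence falls from 18.8% to 17.4%.

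**The case against.** The strongest reply is that width is not an unrelated variable. It is listed among the measurements under the primary outcome and is absent from the secondary outcomes, and the introduction also states a broader aim about scar healing. That is true, and it explains how width came into the calculation. But the outcome named as primary is incidence, and power for one does not carry over to the other.

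Second, 70 may have been reached by using SD 1.0 in both arms and adding 10% for loss, so the fault could be incomplete reporting. That is possible, but the route is not declared and sets aside the SD of 0.6 that the protocol quotes.

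Third, the shortfall for width is conditional. The Outcomes section says measurements are taken for each case, which could mean every woman. On that reading width power is about 94% and the sample is more than enough. On the form's reading it is below 80% unless about 63% of women have a defect. Neither reading gives the stated 80% without an incidence that the protocol omits.

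Fourth, the incidence figures depend wholly on assumed rates and effects, and some combinations are well powered (a halving from 50% or 60%). This stands: the check shows that power for the primary outcome is unknown and could be low, not that the trial is certainly underpowered.

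Fifth, stating the detectable difference for a fixed sample fits the effect to the number. That is a fair limit of the remedy, and is why the text should also say whether such a reduction is expected.

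**Conclusion.** The concern holds and must be fixed. That the stated 80% is not the power of the primary comparison follows from the protocol's own text and needs no assumption. That the width inputs give 43 to 44 per arm, or about 94% power with 70 widths per arm, follows from the stated means and SDs with a two-sided 5% test.

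The size of any shortfall for incidence does rest on assumption, because the protocol supplies no rate. At control incidences of 20% to 60% with no loss, a one-third reduction has 18% to 67% power, and 80% power requires a relative reduction between 75% and 39%.

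**What to change.** Keep 140 women. Under both Sample Justification and Statistical analysis, delete the claim that 140 women give 80% power, and do not keep it relabelled as the power for width. Replace it with:

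- the assumed control-arm incidence of isthmocele at 6 months, with its source;
- the difference in incidence that 70 per arm can detect with 80% power at two-sided 5%, and the same after the expected loss at the 6-month scan;
- a statement of whether a reduction of that size is expected.

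As an illustration only, with an incidence that is not from the protocol: at 40% in the control arm, 70 per arm detect a fall to 18.8% and 60 per arm a fall to 17.4%. Rounding the first to 19% gives 79% power, so the unrounded value should be used.

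If the sponsor also wants a figure for width, it should be a separate, recalculated statement that says how many widths per arm are expected.

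The cost is protocol wording only, with no added patients or procedures. The stated power may become less favourable.

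### Is the primary event left without a depth minimum, so that the isthmocele count depends on who reads the scan?

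*Protocol*

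**What the plan says.** Under Methodology, Outcomes, the protocol names a single primary outcome, the incidence of isthmocele on transvaginal scan six months after birth. The next sentence reads "Isthmocele is defined as an anechoic defect communicating with the endometrial cavity at the anterior wall of the lower uterine segment". A list of measurements follows, among them the depth of the defect, and then notes on shape and residual myometrial thickness. Still ahead of the secondary outcomes, and with a 2012 imaging reference attached, the protocol adds that "the diagnosis of isthmocele was made in case of depth of the defect at least 2.00 mm in the longitudinal plan".

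The Introduction states that "An internationally recognized definition for isthmocele was only agreed upon in 2019 by the European task force" and gives it as an "indentation at the site in the cesarean section scar with a depth of at least 2 mm".

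The case record form has one entry for the six-month scan, "Isthmocele? Yes or NO if Yes", with the measurements to follow when the answer is Yes. It prints no criterion.

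Two secondary outcomes carry their cut-offs inside the definition: fever ("Defined as a temperature higher than 38 c on two consecutive postoperative days") and primary postpartum haemorrhage ("Defined as Cumulative blood loss greater than 1000 mL"). Under Blinding, both the sonographer and the statistical analysis are blind to group.

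**The concern.** The only sentence in the outcome section that defines isthmocele in so many words has no depth limit. The 2 mm sentence is in the past tense and attributed to earlier literature, while the sentences around it describe this trial in the future tense. It could be taken as background rather than as the rule in force. The form does not settle the matter, because the Yes/No call comes before any depth is written down. The authors also placed numerical limits inside two secondary definitions, so the sole primary outcome looks less tightly specified than those.

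If the event rule were truly open, someone holding both an any-depth count and a count at 2 mm or more could choose between them once the results were known. Blinding of the scan and of the analysis guards against a tilt toward one arm, but does not by itself prevent a choice between two rules.

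**Working it through.** **1. Where the two sentences differ.**

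| Finding at the scar | Anatomical sentence alone | Both sentences together |
|---|---|---|
| No communicating anechoic defect | No event | No event |
| Communicating defect, depth 2 mm or more | Event | Event |
| Communicating defect, depth under 2 mm | Event | No event |

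Only the last row is in dispute.

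**2. Which reading the text supports.** The 2 mm sentence stands between the primary-outcome heading and the secondary outcomes. It says when isthmocele is diagnosed, and the primary outcome is the incidence of isthmocele. It speaks of the depth of the defect, which points back to the defect just described. The Introduction gives the same limit as the recognised definition. No passage gives another depth or says that shallower defects count. Tense is weak evidence in a text with loose English throughout, and a citation for a threshold is ordinary: the fever and haemorrhage definitions carry citations too.

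**3. Whether the 2 mm count survives either reading.**
- If the sonographer applies 2 mm when answering, Yes means a depth of 2 mm or more, and the count is the number of Yes answers.
- If the sonographer answers Yes at any depth, depth is measured for every Yes, and the count is the number of Yes answers with depth of 2 mm or more.
- If sonographers differ, applying the depth filter to all Yes answers gives the same count.

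Only the any-depth count can be lost, and it would serve no more than an optional sensitivity analysis.

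**4. Size.** No stated figure in the protocol turns on this point; the sample size was derived from mean defect width, not from incidence. With 70 women per arm, all scanned, each reclassified woman moves her arm's incidence by 100/70 = 1.43 percentage points.

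For a choice made after both results are seen, with two tests at exactly 5% each and no true effect:

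P(at least one significant) ≤ 0.05 + 0.05 = 0.10,

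with a floor of 0.05 when the rules agree for every woman. This bound holds for any pair of 5% tests and uses only the alpha from this protocol.

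An illustration needs assumptions, because the protocol gives neither an incidence nor the share of defects under 2 mm. Take an any-depth incidence of 30% to 70% and 5% to 20% of all women with a defect under 2 mm (70 × 0.05 = 3.5 to 70 × 0.20 = 14 women per arm), with no true effect and 400,000 simulated trials per setting:

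| Test | One fixed rule | Better of the two rules |
|---|---|---|
| Uncorrected chi-square | 4.9% to 5.2% | 7.1% to 9.3% |
| Fisher's exact | 2.5% to 3.5% | 4.7% to 5.9% |

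The protocol names no test, so neither row can be called the trial's own. With Fisher's test the rate stays near 5% even with selection.

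**5. What that inflation needs.** Three things must all happen: the scans are read at any depth, both rules are tested, and the favourable one is kept. If 2 mm is applied at the scan, shallower defects are answered No and not measured, so there is no second count to choose.

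**The case for a change.** The strongest case for a change is that the protocol itself fixes the event, in two statements that classify a 1.5 mm communicating defect differently. That is not detail deferred to an analysis plan. It concerns the only primary outcome, and one sentence plus one form entry from the same scan would remove all doubt.

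Part of this stands. The two sentences are not expressly joined, the form prints no threshold, and a literal reader could count a shallow defect. It is also fair that blinding does not rule out a choice between definitions.

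The rest does not carry. It is too strong to say that the event rule is unfixed, because a depth criterion for the diagnosis sits inside the primary-outcome block and nothing contradicts it. To report an any-depth count as primary, an analyst would have to disregard that criterion and the Introduction together. The low cost of a clarification does not show that the plan as written leads to a wrong result. Nor can the whole specification be seen: the figure that follows the 2 mm sentence is not shown, and the derivation of a binary endpoint from recorded depth is commonly set out in the analysis plan, which is not at hand.

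**Conclusion.** The concern does not call for a change. What remains is a drafting gap confined to communicating defects shallower than 2 mm, and the protocol's own text points to one way of closing it: the anatomical description together with the 2 mm depth. An analyst following the plan would reach that count from the form as it stands.

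No bias between arms follows, since scan and analysis are blind to group, and the count at 2 mm or more is not lost. The number of women affected and any effect on the comparison cannot be derived from the protocol. The ceiling of 10% on the false-positive rate is generic and depends on deliberate selection; the simulated rates rest on assumed incidences, assumed shares of shallow defects and an assumed test. The conclusion itself rests on two things: the 2 mm sentence being read as this trial's criterion, and depth being recorded for every Yes, as the form provides. Joining the two sentences would be tidier wording but would not alter the result.
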